A Preliminary Investigation of Pre-Frontal Repetitive Transcranial Magnetic Stimulation (rTMS) for the Treatment of Cannabis Use Disorder

Statistical Analysis Plan

NCT03144232

June 27, 2023

We calculated descriptive statistics such as means and standard deviations (SD) for all continuous variables and proportions for categorical variables. We compared demographic, screening, blinding, and adverse event variables (compiled using MEDdra criteria) across condition and site using t-tests or the Wilcoxon Rank Sum test for continuous variables and the Chi-Square or Fisher's Exact test for categorical variables.

For Aim-1, we utilized a generalized linear mixed-effects model (GLMM) to perform the analyses, with the full ITT sample (N=72) and the total MCQ-SF score as the dependent measure. We used two types of a priori models for each analysis: 1) a three-way interaction model which included an interaction between treatment, site, and time, as well as the main effects of treatment, site, time, and all pairwise interactions between the main terms, and 2) a two-way interaction model which included treatment, time, an interaction between treatment and time, and site. We considered pre- and post- variables with a strong clinical rationale for inclusion in covariate adjustment including the amount of time since the last cannabis use, CWS score, the days-per-week of cannabis use, the grams of cannabis used per day, and the number of cannabis use sessions per day.

To assess group differences in the number of weeks of abstinence in the follow-up period (Aim-2a), a Poisson regression model was fit with the total number of weeks of self-reported abstinence in the four-week follow-up period as the dependent variable and treatment, site, and treatment by site interaction as independent variables. We conservatively imputed missing values as non-abstinent, thereby including the total ITT sample. We additionally performed a sensitivity analysis for weeks of abstinence by including the weeks preceding the 9th rTMS-treatment visit and immediate post-visit since these two weeks represent the time following the delivery of a total of 16-sessions of rTMS (a similar dose to early rTMS for depression studies). We calculated the relative risk of having a week of abstinence as a measure of the effect size, along with 95% confidence intervals. We used creatinine-corrected urine cannabinoids to verify self-reported abstinence at follow-up weeks 2 and 4, and calculated the proportion that these two methods were concordant.

To evaluate group differences in the number of days of cannabis use (Aim-2b), we utilized a GLMM with the number of days-per-week of cannabis use as the dependent measure. We included participants in the model who had follow-up data (the completer sample; N=51) and given the apparent divergence in days-per-week of cannabis use in the final two-weeks of the follow-up period, we chose to focus our analysis on that period.

Residual normality was assessed for each of the above models using QQ-plots. We included sex in all models to detect a potential effect, but when no significant effects were found, we excluded sex from the subsequent final models. Apart from craving, this was a pilot trial and not powered a priori to detect statistically significant differences; however, statistically significant *p*-values are noted when observed. When reported, a level of $\alpha = 0.05$ was used (two-tailed), and no adjustments for multiple comparisons were made for this preliminary investigation. Effect sizes at each time point were estimated as Cohens d using means and pooled standard deviations. Statistical analyses were conducted using R software (version 4.2.1, GNU project) and SAS version 9.4 (Cary, NC).

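### Aim 1 (craving) is analysed with two models at an unadjusted 0.05, and neither a model nor a treatment contrast is named as the primary test

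*SAP*

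**What the plan says.** The SAP's Aim-1 paragraph sets out a generalized linear mixed model for the total MCQ-SF score in all 72 randomised participants. It continues: "We used two types of a priori models for each analysis: 1) a three-way interaction model", containing treatment, site, time, all their pairwise interactions and the three-way term. The alternative is "a two-way interaction model which included treatment, time, an interaction between treatment and time, and site". Both are called a priori. Neither is called primary, and no coefficient, time point, coding of site or rule for moving between the models is given.

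Two further choices are left open. On covariates: "We considered pre- and post- variables with a strong clinical rationale for inclusion in covariate adjustment", with no rule for the final set. On sex: "when no significant effects were found, we excluded sex from the subsequent final models". The SAP's closing paragraph sets a two-tailed 0.05 with no multiplicity adjustment, and says that craving is the exception to the trial not being powered.

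The 2021 protocol (Section D, Statistical Analysis) does not fill the gap. It compares a final model with an intercept-only model by likelihood ratio, then compares the groups at all planned time points. Neither step isolates one treatment contrast.

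**The concern.** Calling two models a priori fixes the list of candidates but does not choose between them. The two models can also answer different questions. The two-way model's treatment-by-time term is the effect pooled over sites. In the three-way model, what the treatment-by-time term means depends on how site is coded. Under reference-cell coding it is the effect at the reference site alone. Under effect coding, or with a suitable contrast, it is an average over sites. The three-way term is a further p-value, for whether the effect differs between sites.

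With no test named, a reader cannot tell whether a reported p-value is the planned one or the more favourable of several. The 5% error rate in the sample-size justification assumes a single test. If the answer came from a reference-site coefficient, the trial would also have less power than planned, because that coefficient draws on one site's participants.

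**Working it through.** **The plan's own figure.** Inputs from the protocol's Sample Size Justification: difference 8.5, SD 12.2, d ≈ 0.7, 80% power, two-sided 5%, ICC 0.75, attrition 25%.

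- Per arm with independent observations: 2 × (1.960 + 0.842)² / 0.7² = 32.0. The stated 32 matches as a per-arm figure.
- Repeated-measures factor (1 + (m − 1) × 0.75) / m. The number of measurements m is not stated. On 32 it gives 28.0 (m = 2), 26.7 (m = 3) or 26.0 (m = 4). The stated 27 matches m = 3.
- Attrition: 27 / 0.75 = 36 per arm, 72 in total.

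The figure reproduces, and it rests on one pooled active-versus-sham comparison at 5%.

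**Set-up for the two models.** I take one pre-to-post change score per participant, with SD σ, 1:1 allocation within site, normal complete data, no covariates and the same effect at both sites. The protocol's enrolment section gives 43 randomised at the first site and 28 planned at the second, which sum to 71. I use 29 to reach 72. With 28 the error rates are almost the same.

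With n participants split 1:1, the treatment difference has variance 4σ²/n. In units of σ²:

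| Test | Variance | SE |
|---|---|---|
| Pooled (two-way model) | 4/72 = 0.0556 | 0.236 |
| Larger site only | 4/43 = 0.0930 | 0.305 |
| Smaller site only | 4/29 = 0.1379 | 0.371 |
| Site-averaged (three-way model) | ¼ × (0.0930 + 0.1379) = 0.0577 | 0.240 |
| Three-way term | 0.0930 + 0.1379 = 0.2310 | 0.481 |

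**Type I error.** Each test alone has 5%. The error from accepting either of two depends on their correlation under the null.

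- Pooled and site-averaged: correlation √(0.0556/0.0577) = 0.98. Either significant: 5.8–5.9%.
- Pooled and larger-site coefficient: correlation √(43/72) = 0.77. Either significant: 7.9–8.1%.
- Pooled and three-way term: correlation 0. Either significant: 1 − 0.95² = 9.75% (simulated 9.7–9.8%).
- Any of pooled, larger-site and three-way term: 11.3–11.5% by simulation.
- Adding the other site's own estimate as well: about 13%.

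**Power.** I assume a standardised effect of 0.7 on the change score. The noncentrality is 0.7/SE.

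| Test | 0.7/SE | Power |
|---|---|---|
| Pooled | 2.97 | 83% |
| Site-averaged | 2.91 | 82% |
| Larger site as reference | 2.30 | 62% |
| Smaller site as reference | 1.88 | 46% |

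**Sensitivity of the power figures.** The protocol does not say whether its SD of 12.2 applies to a single score or to a change. If 8.5 is a difference in change and 12.2 is the SD of one score with ICC 0.75, the SD of change is 12.2 × √(2 × 0.25) = 8.63 and d = 8.5/8.63 = 0.985. The four powers, in table order, become about 98%, 98%, 89% and 74%. The ordering holds, but the loss is smaller. The type I error figures do not depend on d.

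**The case against.** **The protocol leans towards the pooled question.** This is the strongest reply. Aim 1 in the Specific Aims compares active with sham, after the last session against before the first, with no site element. The Statistical Analysis section lists treatment, time and their interaction, which is the two-way structure. The three-way model then reads naturally as a heterogeneity check in a trial that ran at two sites. That is a fair reading and it supports the remedy below, but neither document says it.

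**The larger error figures need generous counting.** The three-way term tests whether sites differ, not whether active stimulation lowers craving. Calling it a success for Aim 1 would be a stretch. If only the pooled and site-averaged contrasts are eligible, the error is about 6%. This stands: 11% is an upper case, not an expected value.

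**The trial is labelled preliminary, and the lack of adjustment is disclosed.** This softens the consequence but does not remove it for craving, which the SAP sets apart as powered.

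Three stronger readings are tempting and not supported:

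- *That every aim has this problem.* The words about each analysis invite it, but they sit in the Aim-1 paragraph. Aim-2a is one Poisson model of a total count with "treatment, site, and treatment by site interaction as independent variables"; it has no time term, so the pair of models cannot apply. For Aim-2b, "we utilized a GLMM with the number of days-per-week of cannabis use as the dependent measure", but no fixed effects are listed, so the pair is possible and not shown.
- *That the three-way model inherently loses power.* The loss follows from reference-cell coding. The SAP names R and SAS and states no coding.
- *That the more favourable model was selected.* Nothing in the documents shows this.

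**Conclusion.** The point holds for Aim 1. Two models are specified, neither a model nor a contrast is designated, and alpha is unadjusted, so the plan as written does not secure the 5% error rate that its sample size assumes. The excess is small if the three-way model is read through a site-averaged contrast (about 6%), moderate with a reference-site coefficient (8%) or the three-way term (10%), and about 11% if any of the pooled, reference-site and three-way tests counts. The fall in power to 62% or 46% applies only to the reference-site reading, and at a standardised effect of 0.7 on the change score.

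These figures rest on a 43 + 29 split, one pre-to-post change per participant, complete normal data and no covariates. The real analysis could offer more choice: the MCQ is scheduled at baseline, the final rTMS visit and both follow-ups, covariates were only considered, and sex was retained or dropped on significance. None of that was simulated.

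**What to change.** State in the SAP that the single Aim-1 test is the two-way model's treatment-by-time contrast, final rTMS visit against baseline, at a two-sided 0.05. This matches the pooled active-versus-sham hypothesis in the Specific Aims and the comparison used for sizing. Present the three-way model only as a check of site heterogeneity, with an estimate and 95% confidence interval for each site, and state how site is coded.

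The SAP is dated June 2023, is written in the past tense and reports achieved numbers (72 randomised, 51 completers). If results were known when the test is named, label the choice post hoc. Naming it then cannot restore 5% control, so both models should be reported in full for the reader to judge whether the conclusion depends on the model.

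The cost is a few sentences in the SAP and one supplementary table. The sample size and data collection do not change.

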To date there has been limited work examining the effect of rTMS on aspects of CUD. Drawing from the published literature suggesting that excitatory rTMS applied to the DLPFC can reduce craving, the candidate and mentorship team recently completed a preliminary sham-controlled crossover study in cannabis use disordered individuals. The trial suggested that rTMS is safe and well-tolerated, and that a single session of rTMS *acutely* decreases cannabis cue-induced craving. The promising results from our single session trial parallel the single session results found in nicotine and cocaine use disordered populations which subsequently translated into positive multiple session clinical trials(8, 9). As such, it follows that a trial utilizing multiple sessions of rTMS in cannabis use disordered patients may yield positive results.

The overarching goal of this proposal is to investigate if a course of excitatory DLPFC rTMS results in reduced cannabis cue-induced craving in treatment seeking individuals with CUD (Aim1). Additionally, we seek to explore the mechanistic underpinnings of any observed effect by collecting functional magnetic resonance imaging (fMRI) data during cannabis cue-administration before and after the treatment course (Aim 2). These aims will be addressed through a double-blind, randomized, sham-controlled study in which 72 treatment seeking cannabis use disordered participants (36/group) will be given 20 sessions of either *Active* or *Sham* excitatory rTMS applied to the DLPFC. rTMS will be delivered in an accelerated fashion as quickly as in two-weeks, but most often over five-weeks (2 sessions each day, 10 treatment-days). rTMS will be applied in conjunction with a validated three-session Motivational Enhancement Therapy (MET) behavioral intervention.

Aim 1: Determine if a course of excitatory rTMS applied to the DLPFC results in reduced cue-induced craving. We hypothesize that as compared to participants receiving sham rTMS, participants receiving active rTMS will have a reduced level of cannabis cue-induced craving following their final rTMS session as compared to prior to their first rTMS session. We will measure self-reported cannabis craving during a validated cannabis cue-reactivity paradigm, and define cue-induced craving as change in self-reported craving from pre-to-post cue administration.

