Sample Size Justification: The primary focus of this study is to show evidence, with sufficient strength, that treatment with active rTMS will result in decreased cue induced craving (Aim 1), and decreased BOLD response in reward network structures during a cue-reactivity fMRI paradigm (Aim 2) in CUD participants treated with either active or sham rTMS. For Aim 1: Within subject craving measures tend to be highly correlated when measured closely in time and thus we assume a conservative ICC of $p=0.75$ (previous CUD studies range $p=0.60-0.75$) with a standard deviation of ≈ 12.2 . We intend to detect a clinically meaningful craving score difference between the two treatment groups of 8.5 (Cohen's $d=8.5/12.2\approx 0.7$). This is a conservative estimate given that recent multi-session rTMS treatment trials have yielded larger effect sizes on craving ($d=0.98$ (7) in alcohol users, and $d=0.84$ (9) in cocaine users). In the proposed study we will measure increased craving (via MCQ total score) following the presentation of a validated cannabis cue paradigm both before and after a treatment course of rTMS. Under the assumption of independent observations, a total sample size of 32 participants equally allocated to each treatment assignments will provide 80% power with a type 1 error rate of 5% to detect the stated effect size of 0.7. However, the effective sample size in a repeated measures data setting is reduced when assuming an ICC of 0.75. The number of participants per group required is therefore estimated to be $n=27$. Additionally, we need to adjust for study attrition between randomization and the 4-week follow up visit. Assuming an attrition rate of up to 25%, a sample size of **36 participants randomized to each treatment group (n=72 total)** will provide adequate power to detect the primary aim effect size of $d=0.7$ between those receiving active and sham rTMS. **For Aim 2:** In a within subjects investigation of nicotine use disordered participants undergoing a single session of rTMS, there was a significant effect on BOLD response to smoking cues (see figure 2, Preliminary Studies section). If we assume that, as with previous study of cue induced BOLD reactivity in smokers using rTMS, our effects are of medium to large size (e.g. $d=0.7-0.8$) with alpha =5% (2-tailed), a sample of **36 randomized participants in each group will result in greater than 80% power for detecting effects of treatment on CR-BOLD response**. In sum, we are confident that the proposed randomized sample size of 72 participants will be sufficient to test Aims 1 and 2. **For our exploratory Aim**, our recent, non-contingency management based medication trials for cannabis cessation have shown varying placebo abstinence rates (defined as ≤ 50 ng/ml THCCOOH UCT) at the end of study (EOS) treatment (5-15%) (38, 39, 41). Since we are only hoping to provide preliminary data to power a more definitive study, our sample is not designed to sufficiently answer this question definitively. Despite this fact we will still have power to detect a large effect on abstinence. An rTMS abstinence rate of at least 30% greater than placebo at the end of study treatment under the most conservative conditions, at a 10% placebo abstinence rate, a randomized sample size of 36 participants in each treatment group will provide 80% power with a type 1 error of 5% to detect this difference at the end of this pilot study.

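### The Aim 1 models do not use randomised baseline craving to sharpen the treatment comparison, a modest and recoverable loss of precision

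*SAP*

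**What the plan says.** The SAP's Aim-1 paragraph fits a generalised linear mixed model "with the full ITT sample (N=72) and the total MCQ-SF score as the dependent measure". It names two a priori models. One has the three-way interaction of treatment, site and time with all lower-order terms. The other is "a two-way interaction model which included treatment, time, an interaction between treatment and time, and site". Both contain a treatment main effect, and neither states that the arms share a baseline mean. The candidate covariates are described as "including the amount of time since the last cannabis use, CWS score, the days-per-week of cannabis use", followed by grams per day and sessions per day. Baseline craving is not named.

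The protocol's Aim 1 (Specific Aims) hypothesises, for active against sham, a "reduced level of cannabis cue-induced craving following their final rTMS session as compared to prior to their first rTMS session". Its Sample Size Justification says that craving is measured "both before and after a treatment course of rTMS", and the schedule of assessments lists the MCQ at baseline, the final rTMS visit and both follow-up visits. The protocol's Statistical Analysis section says only that characteristics which are imbalanced, associated with the outcome or known to be predictive will be assessed for inclusion as covariates.

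**The concern.** Randomisation makes the two arms' baseline means equal in expectation. A model that estimates them separately and then compares changes from baseline carries the chance baseline difference into the treatment contrast at full weight. The regression of follow-up on baseline would remove only the predictive part of it. Constraining the baseline means to be equal, or adjusting for baseline, gives an estimate of the same effect with smaller variance, from data already in hand.

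What is at stake is the width of the interval and the power of the primary comparison, in a trial planned around 27 evaluable participants per arm. Validity is not at stake.

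**Working it through.** **Inputs** (protocol, Sample Size Justification, unless noted): SD s = 12.2; target difference 8.5; ICC r = 0.75, with 0.60 to 0.75 given as the range in previous studies; 80% power; type 1 error 5%, two-sided according to the SAP; 36 randomised per arm; 25% attrition, leaving 27. Compound symmetry is assumed, with one total MCQ score per visit.

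**The plan's own figures.**
- Independent observations: 2 × (1.96 + 0.8416)² / 0.7² = 32.0 per arm, as stated.
- ICC step: 32 × (1 + 2 × 0.75)/3 = 26.7, so 27. The protocol gives no formula. This one, the variance of a mean of three repeated measures, matches its number; it is not a baseline adjustment.
- Attrition: 27/0.75 = 36, as stated.

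**Complete pairs, 27 per arm.** For each participant, the relevant variance is
- difference in change: 2s²(1 − r)
- equal-baseline or baseline-adjusted: s²(1 − r²)
- ratio: (1 + r)/2

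SE = √(variance × 2/27). Power is for a two-sample t-test at 8.5 points.

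| | r = 0.75 | r = 0.60 |
|---|---|---|
| Change: variance factor | 2 × 0.25 = 0.50 | 2 × 0.40 = 0.80 |
| Adjusted: variance factor | 1 − 0.5625 = 0.4375 | 1 − 0.36 = 0.64 |
| Ratio | 0.875 (12.5% less) | 0.80 (20% less) |
| SE, change to adjusted | 2.35 to 2.20 | 2.97 to 2.66 |
| Power, change to adjusted | 94% to 97% | 80% to 88% |

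The normal approximation gives slightly higher power: 95.2% to 97.2% and 81.7% to 89.2%.

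**Mixed model, 36 with baseline and 27 followed per arm.** The SAP analyses all 72, so participants with only a baseline value contribute. Per arm, in units of s²:
- free baseline means: (1 − r²)/27 + (1 − r)²/36
- common baseline mean: (1 − r²)/27

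At r = 0.75: 0.01620 + 0.00174 = 0.01794, ratio 0.01620/0.01794 = 0.903, or 9.7% less variance. Power (normal approximation) goes from 95.7% to 97.2%.

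At r = 0.60: 0.02370 + 0.00444 = 0.02815, ratio 0.02370/0.02815 = 0.842, or 15.8% less variance. Power goes from 83.6% to 89.2%.

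**If a different contrast was tested.** The SAP names neither the levels of time nor the contrast. If the test were the arm difference at a visit with free means and no baseline adjustment, the complete-data variance factor would be 1, against 0.4375 or 0.64 after adjustment. The direction is the same and the loss larger, but the 12.5% and 20% figures would not apply.

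**The case against.** Treatment, time and their interaction form a standard, valid model, and no type 1 error problem follows from it. At the protocol's ICC of 0.75, power for 8.5 points is already about 94%, so the gain is two to three points. The SAP introduces its covariate list with the word including, so it need not be exhaustive, and the protocol's covariate rule could admit baseline craving. All of this stands. It limits the size of the point but does not remove it: neither document commits to baseline MCQ, and at ICC 0.60, inside the protocol's range, the gain is about eight points of power.

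A reader might infer a far larger loss from the protocol's intention to "define cue-induced craving as change in self-reported craving from pre-to-post cue administration". If all four MCQ readings at the two visits shared a single ICC, the two cue-induced changes would be uncorrelated, and comparing changes against adjusting would give 71% against 94% power at ICC 0.75 and 51% against 80% at 0.60. The documents do not support these as the cost of the SAP's model. That model analyses total MCQ-SF, not cue-induced change. A single ICC treats readings minutes apart like readings weeks apart, although the protocol itself says "Within subject craving measures tend to be highly correlated when measured closely in time". If same-visit readings correlated 0.90 (an assumption), the comparison would be 98% against more than 99%, even with uncorrelated cue changes. The correlation between the visits' cue changes is not given.

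A reader might also infer that Aim-2b ignores baseline use, because the SAP says only "we utilized a GLMM with the number of days-per-week of cannabis use as the dependent measure" and names no baseline term. It lists no fixed effects specific to that model, so omission cannot be concluded from its silence.

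**Conclusion.** The point holds as a modest loss of efficiency in the Aim 1 test; there is no bias and the analysis is not invalid. The variance reduction available is 12.5% to 20% in complete pairs, and about 10% to 16% in the mixed model with the planned attrition, as ICC goes from 0.75 to 0.60. This rests on baseline being a level of time, on treatment-by-time being the tested term, on compound symmetry, and on 12.2 being the SD of a total score. If 12.2 were the SD of a change score, the absolute SEs and powers would differ, but the ratio (1 + r)/2 would not. The gain matters most near ICC 0.60 or for a true effect below 8.5 points. No size is claimed for cue-induced change or for Aim-2b.

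**What to change.** Fit total MCQ-SF with a common baseline mean across arms: time, site, and treatment at each post-baseline time, with no treatment term at baseline. Alternatively, run ANCOVA of final-visit total MCQ-SF on baseline total MCQ-SF, arm and site. Report the adjusted arm difference at the final rTMS visit with its 95% confidence interval, and state the levels of time and the contrast tested.

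The SAP is dated June 2023 and describes analyses in the past tense, so this should not replace the a priori models. Show it beside them as a labelled re-analysis or sensitivity analysis.

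If the protocol's cue-induced change is analysed, adjust the final-visit cue change for the baseline cue change in the same way. That is a separate analysis of a different outcome. For Aim-2b, adding baseline TLFB days per week is a reasonable parallel step if it is not already in the model.

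The cost is some extra model code and a few lines of reporting. No new data are needed, and the equal-baseline constraint relies only on randomisation.

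### The SAP lets post-treatment cannabis use and withdrawal values be candidate covariates for the Aim 1 craving model; an effect adjusted for them need not be the total ITT effect

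*SAP*

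**What the plan says.** The Aim-1 paragraph of the SAP fits a mixed model to total MCQ-SF score in the intention-to-treat sample (N=72). It names two a priori models. One has the three-way interaction of treatment, site and time with all lower-order terms. The other is "a two-way interaction model which included treatment, time, an interaction between treatment and time, and site". Neither lists a clinical covariate.

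The next sentence reads "We considered pre- and post- variables with a strong clinical rationale for inclusion in covariate adjustment". The variables are the time since last use, "CWS score, the days-per-week of cannabis use, the grams of cannabis used per day, and the number of cannabis use sessions per day". The SAP does not say which of these were kept, whether a kept value was pre or post, or which model gives the main Aim 1 result.

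Elsewhere the documents treat some of these variables as outcomes:

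- The Aim-2b paragraph of the SAP uses "a GLMM with the number of days-per-week of cannabis use as the dependent measure".
- The protocol's schedule of visits and assessments lists days of use per week and use sessions per week as secondary substance use outcomes. The SAP covariate is sessions per day.
- The same schedule repeats the Cannabis Withdrawal Scale (CWS) at the final rTMS visit and both follow-up visits.

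The protocol's Statistical Analysis section has its own covariate rule: imbalance at baseline, association with the outcome, or known predictive value. It leans toward baseline characteristics but does not expressly exclude later values. Its sentence on reporting unadjusted and adjusted models follows the abstinence model and may not reach Aim 1.

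**The concern.** Aim 1 asks whether active rTMS, compared with sham, gives a "reduced level of cannabis cue-induced craving following their final rTMS session as compared to prior to their first rTMS session". In the ITT sample that is a total-effect question: everything treatment does to craving counts, including anything that comes about because participants use less or have different withdrawal symptoms.

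Adjusting for use or CWS measured after treatment compares the arms at equal levels of something treatment may have changed. The protocol itself, in its section on potential benefits, allows that rTMS may reduce use. The adjusted contrast would then leave out the part of the effect that runs through the covariate. If unmeasured factors drive both later use and craving, randomisation no longer protects the contrast either. The confidence interval would show neither problem.

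This matters most for craving, because the SAP says "Apart from craving, this was a pilot trial and not powered a priori to detect statistically significant differences". Craving is the one outcome it describes as powered.

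**Working it through.** **1. What pre and post refer to.** A before-cue and after-cue reading does not fit, because days per week and grams per day cannot change within a cue session. Before and after treatment is the natural reading.

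**2. The plan's own figures** (protocol, Sample Size Justification). Difference 8.5, SD 12.2, so d = 8.5/12.2 = 0.70, as stated. ICC 0.75. With 27 per group and 25% attrition, 27/0.75 = 36 per group, as stated. The plan gives no figure for covariate adjustment, so nothing further can be reproduced.

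**3. The principle, in SD units (all values assumed).** Let treatment lower post-treatment use by 0.5, let each unit of use raise craving by 0.4, and let the direct effect be -0.50.

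- Total effect: -0.50 + (-0.5 × 0.4) = -0.70.
- A simulation of 400,000 subjects gave -0.70 with baseline covariates only and -0.50 once the post value was added.
- With an unmeasured factor behind both use and craving, the post-adjusted value was -0.37.
- With no treatment effect on the covariate, it was again -0.70.

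**4. Illustration on the protocol's scale.** Two visits (pre, post); random-intercept model with treatment, time, their interaction, and use at each visit; site omitted. From the protocol: SD 12.2, pre-post correlation 0.75, effect 8.5. Assumed: use in SD units with pre-post correlation 0.5, same-visit correlation r between MCQ and use, cross-visit correlation 0.75r, and treatment lowering use by k SD.

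Adjusted effect = 8.5 − slope × k. To get the slope, split the two visits into a sum and a difference, each divided by √2. For r = 0.5:

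- Use variance: 1.5 (sum), 0.5 (difference).
- Covariance with MCQ: 12.2 × (0.5 + 0.375) = 10.675 and 12.2 × (0.5 − 0.375) = 1.525.
- Separate slopes: 10.675/1.5 = 7.12 and 1.525/0.5 = 3.05.
- Residual variance at the solution b = 4.43: 148.84 × 1.75 − 2b × 10.675 + 1.5b² = 195.3, and 148.84 × 0.25 − 2b × 1.525 + 0.5b² = 33.5.
- Weights: 1.5/195.3 = 0.00768 and 0.5/33.5 = 0.0149.
- Weighted slope: 4.43 points per SD of use.

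| r | slope | k = 0 | lowered 0.1 | lowered 0.3 | lowered 0.5 | raised 0.5 |
|---|---|---|---|---|---|---|
| 0.3 | 2.59 | 8.50 | 8.24 | 7.72 | 7.20 | 9.80 |
| 0.5 | 4.43 | 8.50 | 8.06 | 7.17 | 6.28 | 10.72 |
| 0.6 | 5.46 | 8.50 | 7.95 | 6.86 | 5.77 | 11.23 |

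The last column is the case where treatment raises the covariate, which is possible for CWS.

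**5. Sensitivity at r = 0.5, use lowered 0.5 SD.** A use pre-post correlation of 0.3 to 0.7 gives 6.66 to 5.68. A cross-visit correlation of 0.2 to 0.45 gives 4.94 to 6.66. The lowest value is a shift of (8.5 − 4.94)/8.5 = 42%.

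Neither r nor k is in the documents, so these values are examples and not bounds.

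**The case against.** The strongest reply is that no document shows the problem occurred. The SAP says these variables were considered. It does not say that any entered, that a post value entered, or that an adjusted model is the Aim 1 result. Both a priori models leave them out, and the plan states "Effect sizes at each time point were estimated as Cohens d using means and pooled standard deviations", which appears to be an unadjusted calculation. All of this stands. A reader might infer that the Aim 1 result is already distorted; the documents do not support that.

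A reader might also take the Aim-2b wording, "given the apparent divergence in days-per-week of cannabis use in the final two-weeks of the follow-up period", as evidence that treatment did change use, and so that adjusted craving contrasts at follow-up are affected. It does not show this. The phrase gives neither direction nor size, the analysis is in completers (N=51) and not the 72, and the window was chosen after the data were seen. The Aim 1 hypothesis concerns the period from before the first to after the final rTMS session, and the documents do not say whether use had changed by then.

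The outcome overlap is documented only for days and sessions of use. Time since last use, grams per day and CWS are not named as outcomes. That narrows the supporting text but not the principle, since their post values are still measured after randomisation.

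What survives is the rule itself. As written, it admits covariates that can turn an ITT contrast into a different one, and the plan does not say whether that happened.

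**Conclusion.** The concern holds in a limited form. The SAP's covariate rule for Aim 1 admits post-treatment values of five variables. A treatment effect adjusted for any of them is not the total ITT effect if treatment changes that variable. The two a priori models and the Cohen's d values, as described, are outside the concern.

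Neither size nor direction can be computed from the documents. If treatment does not affect the covariate, the planned 8.5 points stay at 8.5 whatever the correlation. In the assumed cases above they fall to about 5 or rise to about 11. It would therefore be wrong to infer that adjustment must shrink the effect or cost power. The illustration rests on a linear two-visit model without site, the protocol's SD and ICC, and assumed values for everything that concerns the covariate.

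**What to change.** 1. Restrict covariate adjustment of the Aim 1 treatment effect to pre-randomisation values of the five listed variables.
2. Name one of the two existing a priori models as the main Aim 1 result.
3. State which covariates, if any, entered an adjusted Aim 1 model and whether each was a pre or post value. If a post value was used, re-fit with the baseline value.
4. Label any model that contains post-treatment use or CWS as exploratory or mediation.

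The cost is a short SAP edit and, only if a post value was used, one re-fit on data already collected. The sample size does not change.
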